
**Note:** This study will use the NIDA SREC, which is currently modeled after NJOY's commercial e-cig product, the Ace. This device will be used in research studies via an Investigational Tobacco Product (ITP) designation.

On April 4, 2018, the FDA issued a Letter with No Concerns regarding the ITP application that was submitted concurrently with the original IRB application. The study was initiated, but temporarily suspended while modifications to the SREC product were made. As such, a new ITP application was submitted at the time of the January 2021 IRB amendment and a second Letter with No Concerns was issued on March 26, 2021.

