### ii. Randomization process

Participants will be randomized to one of four groups. This design allows for a rolling admission and increased contemporary controls in the event a device is not available at the time of enrollment. The conditions subjects are randomized to may vary depending on product availability. Within each group, we will also randomize the patients to sequence the right or left lung for the baseline bronchoscopy in an approximate 1:1 ratio. These patients will then receive a second bronchoscopy in the opposite lung at ~71 days in order to reduce the influence of the baseline procedure at follow-up. The randomization procedures will be supervised by the biostatistician.

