- 2) Descriptive statistics and clustering (e.g., principal components analysis [PCA]), will be performed for all biomarker data measured at the different visits. Baseline data (1st bronchoscopy) will then be compared between the four groups (3 conditions and control) using a one-way analysis of variance (ANOVA). The non-parametric Kruskal-Wallis test (continuous or ordinal variables) or the chi-square test (categorical variables) will be applied when the normality assumption of the data is not met. We will compare controls to complete substitution with the SREC (with and without nicotine) or NRT. Generalized linear models (GLM) will be employed with measurement (cell count, gene expression, etc.) as the dependent variable, a covariable for baseline measure, and a main effect of arm. Other relevant variables that are associated with the biomarker results, e.g., baseline smoking, Fagerstrom Test for Nicotine Dependence (FTND), or gender will also be included in our models as they are potential confounders. We also will assess batch effects and include batch as a co-variable in the model (all samples will be analyzed at the same time, except for cell counts). We plan to use baseline molecular measurement as a covariable rather than

modeling the change between baseline and follow-up because the former is more powerful [1]. Given the large dynamic range of the cell count and the 'omics data, we will initially consider a normal distribution. If the data are determined to deviate from normality, we will log-transform the data or assume a non-normal distribution of residuals (such as Poisson) for the GLM. Urine propylene glycol (PG) will be measured at the 2nd bronchoscopy visit and compared to baseline to verify e-cig use. As an exploratory analysis, urinary PG will be used as the exposure predictor variable assessing the biomarker results as dependent variables. Urine anatabine, urine anabasine and nicotelline will be used to confirm complete substitution or a predictor variable for smoking reduction. The cotinine level will be used as a surrogate for smoking reduction.

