
methylation levels and corresponded cytokines. Correlations controlling for possible confounders (e.g., age) will be explored using multiple linear regression models. We will also explore if the correlation between methylation and cytokine levels may be mediated by gene expression of cytokines using interaction analysis.

- 3) To compare treatment groups at follow-up for inflammatory markers and 'omics data, we will use generalized linear models (pairwise) with a covariable for baseline measure to account for baseline differences:

$$\text{Model 1: Followup_Measure} = \text{Baseline_Measure} + \text{arm} + e.$$

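### The primary model omits lung side and the set of arms open at randomisation: the first costs precision, and the second can bias contrasts if an arm closes while controls keep enrolling

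*SAP*

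**What the plan says.** **Model.** SAP item 3 compares groups at follow-up: "we will use generalized linear models (pairwise) with a covariable for baseline measure to account for baseline differences". The equation, Model 1, has a baseline term, an arm term and an error. SAP item 2, and the matching text in Protocol section 4.g.i, describes the same model more fully. It adds batch and "Other relevant variables that are associated with the biomarker results, e.g., baseline smoking, Fagerstrom Test for Nicotine Dependence (FTND), or gender". It also notes that "all samples will be analyzed at the same time, except for cell counts".

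**Open arms.** Protocol section 4.a.ii says: "The conditions subjects are randomized to may vary depending on product availability". It adds: "This design allows for a rolling admission and increased contemporary controls in the event a device is not available at the time of enrollment". The note in Protocol section 1 records that the study began and was then "temporarily suspended while modifications to the SREC product were made".

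**Lung side.** The same Protocol section 4.a.ii says that within each group "we will also randomize the patients to sequence the right or left lung for the baseline bronchoscopy in an approximate 1:1 ratio". The opposite lung is sampled at the second bronchoscopy, around day 71.

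Neither document names lung side, enrolment period or the set of open arms as a term in any model. Neither restricts a contrast to participants who were randomised while both of its arms were available.

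**The concern.** An analysis should normally reflect how participants were randomised. Two features of the randomisation are missing here.

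*Open arms.* A control who enters while a device is unavailable could not have been allocated to that device. That person is not a randomised comparator for the device arm, and pooling them with concurrent controls lets calendar-time drift enter the contrast. Drift is plausible. The 09/19/2022 entry in the revision history widens eligibility (age up to 52, at least 5 cigarettes a day) and adds respondent-driven recruitment. Cell counts, which carry the power calculation, are the one assay not run together.

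*Lung side.* Baseline and follow-up come from opposite lungs, so any right-left difference raises one measurement and lowers the other. If side is not in the model, this variation inflates the residual and weakens the baseline covariate.

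At stake are a possible bias in the first case and lost precision in the second, in a trial that plans on 21 evaluable participants per arm.

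**Working it through.** **The plan's own figure.** Inputs from Protocol section 4.g.ii and SAP item 3: 21 per arm, two-sided alpha 0.0001, 80% power, CV 0.26, two-sample t-test. On the log scale, SD = √ln(1 + 0.26²) = √0.0654 = 0.256. The detectable difference is 1.613 SD, and exp(1.613 × 0.256) = 1.51-fold. The stated 1.5-fold is reproduced. It uses neither lung side nor enrolment period.

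**Lung side.** The documents give no right-left difference and no baseline to follow-up correlation. I assume ρ = 0.5 and a difference of 1.1- or 1.2-fold, d on the log scale. CV 0.26 is the plan's assumption. CV 0.61 follows from the smokers' cell counts in Protocol section 4.g.ii (1.48/2.41).

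With σ² = ln(1 + CV²) and side balanced:
- variance of each measurement, V = σ² + d²/4
- covariance of baseline and follow-up, C = ρσ² − d²/4
- residual variance without side = V − C²/V (least squares re-estimates the slope)
- residual variance with side = σ²(1 − ρ²)

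| CV | Right-left difference | Without side | With side | Ratio |
|---|---|---|---|---|
| 0.26 | 1.1-fold | 0.0540 | 0.0491 | 1.10 |
| 0.26 | 1.2-fold | 0.0657 | 0.0491 | 1.34 |
| 0.61 | 1.1-fold | 0.2423 | 0.2373 | 1.02 |
| 0.61 | 1.2-fold | 0.2555 | 0.2373 | 1.08 |

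In terms of power at 1.5-fold (CV 0.26, ρ = 0.5, alpha 0.0001), a difference of 0.5 SD, which is exp(0.5 × 0.256) = 1.14-fold, gives 85.2% without side and 92.6% with it. If there is no right-left difference, adding the term moves power from 92.8% to 92.6%. Side is randomised within group, so the arm estimate is unbiased either way.

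**Open arms.** The documents give no closure share and no drift. Let p be the share of controls who are non-concurrent, δ the log drift and b the fitted baseline slope.
- Drift at follow-up only: bias = p × δ. With p = 1/3 and δ = ln 1.2 = 0.182, this is 0.061 on the log scale, about 6%.
- Drift at both visits: bias is about p × δ × (1 − b). With b about 0.5, this is 0.030, about 3%.
- No closure: p = 0 and the bias is 0.

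Simulation of Model 1 with no true arm effect, 21 per arm, ρ = 0.5 and 1.25-fold drift, tested at a nominal two-sided 5%:

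| Non-concurrent controls | Drift | Mean ratio | Type I error |
|---|---|---|---|
| 25% | follow-up only | 0.95 | about 11% |
| 50% | follow-up only | 0.90 | about 28% |
| 25% | both visits | about 0.98 | about 6% |
| 50% | both visits | about 0.95 | about 9% to 10% |

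Adding a period term returns the ratio to 1.00 and the error to about 5%.

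**The case against.** The strongest reply is that the plan is fuller than the Model 1 equation. Item 2 puts batch in the model and admits other variables associated with the outcome, so it would be wrong to say that the plan adjusts for baseline and arm alone. Batch also bears on drift in cell counts. This stands. But batch is a laboratory variable and at best a rough stand-in for which arms were open. A rule that admits variables because they turn out to be associated with results is data-driven and guarantees neither term.

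A reader might infer that the randomised comparison is already broken. The documents do not show that. The protocol says conditions may vary. The one recorded product interruption suspended the whole study, which is not the same as enrolling controls alone. Nothing says whether participants on an earlier SREC version count among the 128.

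A reader might also infer that omitting lung side biases the results. Randomising side within group rules that out. The point has no bearing on urine, blood, nasal or FeNO measures.

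Finally, a reader might take pairwise fitting itself as an error, because a pooled four-arm error term has more degrees of freedom: 77.7% power at 40 df against 84.2% at 80 df for an unadjusted t-test at 1.5-fold. That gain assumes equal variances. The group figures in Protocol section 4.g.ii imply CVs of 1.48/2.41 = 0.61 and 4.84/4.03 = 1.20. The log variances are then 0.32 and 0.89, a ratio of about 2.8. Pairwise fitting is a defensible trade-off.

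**Conclusion.** The point holds in a limited form. Both lung side and the set of open arms belong to the randomisation scheme, and neither is prespecified in the analysis.

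For lung side the loss is precision in BAL and bronchial-brushing outcomes. Under the stated assumptions it is about 10% to 34% extra residual variance at CV 0.26 and 2% to 8% at CV 0.61. It is negligible if the lungs hardly differ.

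For open arms the risk is bias, and it is conditional. It needs an arm to close while controls accrue, together with drift that baseline and batch do not absorb. In the illustrative case it is 3% to 6%. It is zero if no arm closes, and the documents show no closure under the four-arm design. Because the protocol expressly allows closure, the handling should be settled before outcome data are examined.

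**What to change.** 1. Reconcile SAP items 2 and 3 into one stated model. Keep baseline and batch, and name the other covariates in advance. Keep each outcome on its own scale or distribution: a single log-log model would not suit the Poisson model for mtDNA mutation counts or the methylation M-values, which can be negative.
2. Add lung side at follow-up as a fixed covariate for BAL and bronchial-brushing outcomes only. Protocol Table 1 already lists a lung randomisation record.
3. State what happens if any arm is closed for a period, or if the SREC version changes among analysed participants. Either add a stratum for the set of open arms and SREC version, or restrict each contrast to participants randomised while both of its arms were open. Table 1 lists no field for this, so derive the stratum from randomisation dates set against a dated record of product availability. If nothing closed or changed, the term drops out.

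Pairwise fitting may stay. The cost is SAP wording, a few degrees of freedom, and possibly a few controls left out of some contrasts.

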## **ii. Sample Size and Power**

We will enroll 128 subjects (32 per group). For power calculations, we will use a planned 66% retention rate at 5 weeks, based on the clinical trial discussed above, and knowing that we have a 100% retention for never smokers receiving serial bronchoscopies. Thus, the final sample size will be 21 subjects per group ( $n=84$ ) For the purposes of sample size considerations, we will consider cell counts based on the current available data in the cross-sectional study comparing smokers to e-cig users, as indicated above. Based on our current data of smokers undergoing bronchoscopy, the mean cell count for the smokers was  $2.41E+07$  ( $1.48E+07$ ) and the e-cig users was  $4.03E+07$  ( $4.84E+07$ ). In the preliminary cross-sectional study, we see decreases in cell counts of

~2.5 fold with e-cig use. For our power calculations we will assume a CV = 0.26 (from the healthy smokers undergoing bronchoscopy). For power, because of the large number of tests (the total number is currently unknown because of unknown numbers of metabolites and gene expression passing filtering), we will assume a significance threshold that corresponds to one expected false discovery per 10,000 tests (0.0001). Thus, for a final sample size of 21 in the control group and 21 in each use condition, for a two sided analysis, we have 80% power to detect  $\geq 1.5$ -fold difference in cell counts/cytokine levels between each condition and controls for a two-sample t-test. For gene expression/metabolomics/proteomics data, with the same considerations except a CV=0.5 (approximate from many gene expression data sets with which we have worked), we have 80% power to detect  $\geq 2.1$ -fold differences.

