Power is provided for a t-test [2]. Expression/metabolomics/proteomics data tend to follow Gaussian distributions, although there can be violations within each platform. With the large number of variables present in 'omics data, it is intractable to evaluate the appropriateness of the model for each individual variable. Therefore, we use the overall distribution across all variables within a platform to assume a distribution. While individual variables may randomly deviate from the model assumptions (normality, in most cases), if the overall distribution is Gaussian we assume that each of the features was sampled from the overall Gaussian. However, to check if assumptions are causing spurious positive results, we will test each associated feature, post hoc, for departures from the model assumptions. Cell counts were also considered Gaussian for these power calculations. While counts are inherently discrete, because the expected cell counts are very large ($>2E+07$), Gaussian should be a good approximation for this distribution. The parameters included in the power calculation are the CVs, the p-values, and the effect sizes. The CVs used were estimated from preliminary data (and similar data from other studies). The effect sizes assumed are reasonable (smaller) compared to the effect sizes we see in the preliminary data. The p-values used were stringent to adjust for multiple comparisons. Because, especially with 'omics data, we do not know a priori the number of tests, we use significance thresholds that correspond to an expected number of false discoveries per number of tests to control for multiple comparisons without defining the number of tests. For the primary analyses, we accept that one expected false discovery per 10,000 tests is a reasonable error rate. In practice, we will use FDR to determine the expected fraction of false discoveries for assuming a particular significance threshold. For a final sample size of 21 in the control group and 21 in each use condition, for a two-sided analysis, we have 80% power to detect ≥ 1.5 -fold difference in cell counts/cytokine levels between each condition and controls for a two-sample t-test. For gene expression/metabolomics data, with the same considerations except a CV=0.5 (approximate from many gene expression data sets with which we have worked), we have 80% power to detect ≥ 2.1 -fold differences.

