- 4) For mtDNA features, Model 1 is also used. CN is expected to be Gaussian, while mutation rate is expected to be low counts; therefore, a t-test was powered for CN and Poisson [3] for mutation rate. Because there will only be several comparisons here, the significance threshold used for power corresponds to one expected false discovery per 100 tests. We believe that this threshold is a good balance between potential Type I and Type II errors, given the number of tests. The coefficient of variation was calculated from results in the

literature, as cited in the main body of the protocol. For CN, with 21 samples per group, considering a significance threshold of 0.01, a two-sided, two-sample t-test achieves 80% power to detect an 1.4 fold difference between arms considering a coefficient of variation of 0.32 [4]. For mutation, Poisson regression achieves 80% power to detect a mutation rate ratio of 2.7 between arms considering a significance threshold of 0.01 and 21 samples per group [5].

- 5) For associations between mtDNA and other 'omics features, we assume the regression model [6]:

$$\text{Followup_Expression} = \text{Baseline_expression} + \text{arm} + \Delta\text{mtDNA feature} + e,$$

Where $\Delta\text{mtDNA} = \text{Followup_mtDNA} - \text{Baseline_mtDNA}$. We consider this model across all arms. The effect of arm is included as a covariable to ensure that associations are not simply due to both features being associated with arm; rather, we are looking for a more direct relationship. Again, we consider a significance threshold corresponding to one expected false discovery per 10,000 tests, as described above. To generalize, we assume unit standard deviations of the dependent and independent variables (each feature will have a different standard deviation, so results are calculated in terms of standard deviations). With 84 samples, considering a significance threshold of $p=0.0001$ and unit standard deviations for dependent variable residuals and ΔmtDNA features, linear regression achieves 80% power to detect a slope of 0.48.

- 6) For comparing mtDNA features between nasal and bronchial samples, mixed Poisson or mixed Gaussian will be employed with a random effect for subject, and a main effect for location (bronch vs. nasal):

$$\text{Feature} = \text{sample\&rand} + \text{location} + e.$$

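### The plan lets the data choose the analysis scale for cell counts, and one of the two fallbacks it offers, a Poisson model, is invalid for counts of this size

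*SAP*

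**What the plan says.** SAP item 2 and protocol section 4.g.i (Data Analysis Plan) cover the cell counts and the 'omics data together: "we will initially consider a normal distribution". If the data turn out not to be normal, they are to be log-transformed, or else a non-normal residual distribution is to be assumed in the GLM, with Poisson as the one example. No normality test, threshold or rule for choosing between the two is stated. A log2 transform is fixed in advance only for the 'omics data.

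SAP item 3 gives the power for a "fold difference in cell counts/cytokine levels between each condition and controls for a two-sample t-test", with 21 per arm. It states that "Cell counts were also considered Gaussian for these power calculations" and argues that counts above 2E+07 are large enough for a Gaussian approximation. Protocol section 4.g.ii supplies the spread: "For our power calculations we will assume a CV = 0.26". For mitochondrial DNA, SAP item 4 states: "CN is expected to be Gaussian, while mutation rate is expected to be low counts". Copy number is powered for 1.4-fold at CV 0.32 and alpha 0.01.

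Neither document says whether the t-test behind the fold differences is on the raw or the log scale.

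**The concern.** Two things follow from the rule as written.

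- **The estimand is left open.** A normal model on raw counts reports a difference in means. A log transform reports a ratio of geometric means. A Poisson model with its usual log link reports a ratio of arithmetic means. Which of these is reported for total cell count would be settled after the data are seen.
- **One permitted branch is unsound.** A Poisson model fixes the variance equal to the mean. BAL cell counts differ between people by a large fraction of the mean, so at tens of millions of cells the model would take almost all between-subject variation for signal. An analyst could choose this branch and still be following the plan.

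The Gaussian argument in SAP item 3 does not settle the scale. A large count makes the counting error approximately normal, but it says nothing about the shape of the distribution between subjects.

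**Working it through.** **Inputs.** 21 per arm, two-sided. Cell counts: 1.5-fold, CV 0.26, alpha 0.0001 (SAP item 3, protocol 4.g.ii). Copy number: 1.4-fold, CV 0.32, alpha 0.01 (SAP item 4). Tissue-by-arm interaction: 1.5-fold, CV 0.32, alpha 0.01/6 (SAP item 7). Pilot smokers: 2.41E+07 (1.48E+07); pilot e-cig users: 4.03E+07 (4.84E+07) (protocol 4.g.ii). The bracketed figures are not labelled; I read them as SDs.

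**1. The plan's power figures.** With the noncentral t on 40 df, 80% power needs a standardised difference d of 1.613 (cell counts), 1.101 (copy number) and 1.312 (interaction).

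- Log scale: SD = sqrt(ln(1 + CV²)), which is 0.2558 at CV 0.26 and 0.3122 at CV 0.32. Detectable fold = exp(d × SD):
  - cell counts: exp(1.613 × 0.2558) = 1.511
  - copy number: exp(1.101 × 0.3122) = 1.410
  - interaction: exp(1.312 × 0.3122) = 1.506
- Raw scale, same CV in both arms: solve d = (f − 1) / (CV × sqrt((1 + f²)/2)). This gives f = 1.546, 1.436 and 1.547.

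To one decimal, both scales return the printed 1.5, 1.4 and 1.5. At exactly the printed folds, power for cell counts and copy number is 77.7% and 77.9% on the log scale, and 70.4% and 73.1% on the raw scale under normal data. About 2 points of the shortfall from 80% is therefore rounding of the fold.

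The 'omics figure (2.1-fold, CV 0.5, alpha 0.0001) does separate the scales: log gives 2.14 and raw gives 2.58. But those data are stated to be log2-transformed.

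**2. What the data-driven choice costs in power.** Simulation of 20,000 lognormal trials, using a Shapiro test at 0.05 on the 42 residuals as an assumed trigger for the log transform:

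| | always raw | always log | raw, log if flagged |
|---|---|---|---|
| Cell counts | 72.6% | 77.8% | 77.0% |
| Copy number | 74.8% | 77.8% | 78.1% |

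Always-raw costs 5.2 and 3.0 points. The log fallback recovers nearly all of this, although the test flags only about 36% and 47% of trials.

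**3. The Poisson branch for total cell counts.**

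- Poisson SD at the pilot mean: sqrt(2.41E+07) = 4,909.
- SD at the assumed CV: 0.26 × 2.41E+07 = 6.27E+06, which is 1,276 times the Poisson SD. The pilot figure of 1.48E+07 is 3,015 times the Poisson SD.
- If the arms are identical, the model-based z statistic has an SD of about 1,276 instead of 1. The two-sided critical value at alpha 0.0001 is 3.891. The chance of not rejecting is about 2 × 0.399 × 3.891/1,276 = 0.0024, so the test rejects a true null about 99.8% of the time.
- With the pilot ratio of 3,015, the same step gives about 99.9%.
- Baseline adjustment does not help. At an assumed baseline correlation of 0.6, the residual SD is multiplied by sqrt(1 − 0.36) = 0.8 and the ratio is still 1,021, with rejection about 99.7%.

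**4. Why log is the natural scale.** Taken as a mean and SD, the pilot e-cig figures would put Φ(−4.03/4.84) = 20% of a Gaussian below zero cells.

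**The case against.** The strongest reply is that the plan already protects its power. If the data are clearly skewed, the log transform is available. If the skew is too mild to notice, raw analysis costs little. The simulation supports this. Baseline adjustment, which the printed power ignores, helps further: for raw-scale ANCOVA on lognormal data, an assumed baseline correlation of 0.4 (not given in the documents) brings power to about 81% for both outcomes. The SAP sentence on Gaussian counts is also limited to the power calculation, and item 3 adds a post hoc check of model assumptions for associated features. All of this stands.

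A reader might therefore infer too much in three ways.

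- *That the printed power cannot be obtained on the raw scale.* At the printed precision it can, under a constant CV. The 'omics figure, and the wording that the same considerations apply apart from the CV, suggest that one log-scale method was used throughout. That remains an inference.
- *That the trial will be analysed raw and lose substantial power.* Normality is only the starting assumption, so an always-raw analysis is not what the plan prescribes.
- *That a decrease makes the loss far larger.* This follows only if the control arm's SD is carried over to an arm with a lower mean. At a 1.5-fold decrease that raises the lower arm's CV from 0.26 to 0.39. It is a different variance assumption and not an effect of scale.

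In defence of Poisson, it is offered only as an example, and robust or quasi-Poisson errors would remove the false rejections. The plan specifies neither, and it does not exclude cell counts from the option.

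**Conclusion.** The point holds as a fault in the analysis rule, and it should be corrected before analysis. For cell counts, the scale and the effect measure depend on the observed data through an unspecified criterion, and one permitted branch is invalid. If the Poisson branch were taken with model-based errors, about 99.8% of null comparisons of total cell count would be significant at alpha 0.0001. That figure assumes a CV of 0.26, a mean of 2.41E+07 and no correction for overdispersion; it barely changes at the pilot spread or after baseline adjustment.

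The power consequence is small: about 3 to 5 points for an always-raw analysis of lognormal data, and about 1 point or less under the plan's own log fallback if a Shapiro-type check triggers it. The documents do not support a claim of serious power loss or of an irreproducible sample size. Poisson for mtDNA mutation counts, which the SAP expects to be low, is a separate matter and is not criticised here.

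**What to change.** In SAP items 2 to 4 and protocol section 4.g:

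- State that total and differential cell counts, cytokines and mtDNA copy number are analysed on the log scale, with log baseline as covariate and arm effects reported as ratios of geometric means with confidence intervals.
- Remove the provisional normal model and the data-driven switch for these outcomes, and delete the Poisson alternative for cell counts.
- State a small fixed offset for zero counts in rare cell types.
- Label the power figures as log-scale. Give the detectable folds at 80% power as about 1.51 for cell counts and 1.41 for copy number, under the stated CVs and 21 per arm.

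The cost is wording only: no change to sample size, assays or visits, and almost no power given up against the present rule. Raw-scale means can still be shown descriptively.
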